5.0 ETHICAL CONCERNs	16
5.1 Human Subjects	16
5.1.1 Institutional Review Board	16
5.1.2 Confidentiality, Risks, and Risk Minimization	16
5.1.3 Benefits to Participants	17
5.1.4 Costs and Compensation	17
5.1.5 Informed Consent	17
5.2 Adverse Event Reporting	18
5.3 Study Discontinuation	18
6.0 PUBLICATION AND DISSEMINATION OF RESEARCH FINDINGS	18
7.0 WORKPLAN	20
7.1 Project Management	20

8.0 BUDGET	21
9.0 REFERENCES	22

HISTORY OF PROTOCOL CHANGES

Version 1.0, 9 August 2018

- None to date.

Version 1.1, 07 November 2018

- Changed titled to: The Sub-Saharan Africa Regional Partnership (SHARP) for Mental Health Capacity Building – A Clinic-Randomized Trial of Strategies to Integrate Depression Care in Malawi
- Added sample size justification
- Revised objectives
- Updated list of sites
- Discussion of risks related to recording and to blood collection
- Removed “not” from “These recordings will NOT be identified with a code number” on pages 14 and 15

Version 1.3, 04 December 2019

- Changed patient interview follow-up schedule from 3 and 9 months to 3, 6 and 12 months

Version 1.4, 20 February, 2020

- Made follow-up schedule consistent across protocol (interviews during Year 3)
- Added to Year 3 qualitative interview population (added 6 Clinical Coordinators, 6 Friendship Bench counselors, and 6 SHARP research assistants to the existing population of 6 clinic directors, 6 providers, and 3 MOH administrators)
- Reduced sample size for patient qualitative interviews from 16 to 8

Version 1.5, 19 March, 2020

- Amended interview format to include phone calls

Version 1.6, 30 September, 2020

- Added to Year 3 qualitative interview population (added 6 more providers for a total of 12)

Version 1.7, 26 February, 2021

- Added to Year 3 cognitive interviews and structured surveys to evaluate providers' perceptions of stigma and acceptance towards individuals with mental health disorders.

Version 1.8, 1 September, 2021

- Added Year 4 qualitative interviews with hospital workers and SHARP research assistants following results of Year 3 qualitative interviews

Version 1.9, 11 November 2022

- Removed Dignitas International personnel from protocol team roster
- Updated statistical analysis plan to replace generalized linear models with generalized estimated equation models.

PROTOCOL TEAM ROSTER

UNC Principal Investigators

[name], MPH
UNC School of Public Health
Department of Epidemiology
[name]
[name]

1.0 INTRODUCTION

Despite the heavy burden of mental illness, the mental health treatment capacity of most sub-Saharan African health systems is extremely limited. Although effective mental health treatment interventions are well defined in high-income countries, their deployment in low- and middle-income countries is limited due to lack of implementation science research that addresses the challenges of adapting evidence-based interventions to low-resource contexts and few researchers and policymakers adequately trained in implementation science. The Sub-Saharan Africa Regional Partnership (SHARP) for Mental Health Capacity Building seeks to make a meaningful impact on the mental health treatment gap in sub-Saharan Africa. The partnership brings together governmental, academic, and non-governmental partners invested in mental health research and treatment. SHARP will conduct critical implementation science research and build capacity among researchers and policy makers to facilitate scale-up of evidence-based mental health treatment in Malawi, Tanzania, and sub-Saharan Africa.

1.1 Background and Literature Review

Mental health disorders, including depression, contribute substantially to global disease burden, disability and mortality. Mental health disorders are the leading cause of years lived with disability (YLD) (31.7%) and the fifth leading cause of global disability-adjusted life years (DALYs) (7.4%).[1, 2] Depression contributes more to this burden than any other mental health condition. A recent review indicates that mental disorders are associated with significantly increased mortality; a median of 10 years of potential life is lost due to mental disorders, and 14.3% of deaths worldwide (approximately 8 million) can be attributed to mental disorders.[3] Globally, more than 2.2 million excess deaths annually can be attributed to depression.[4] Across regions, sub-Saharan Africa suffers from the highest cost of years of life lost due to mental disorders.[1] At the same time, the capacity of many low- and middle-income countries (LMICs), and especially many sub-Saharan African countries, to respond to this mental health burden is severely limited.[5] The median number of mental health professionals per 100,000 population among sub-Saharan African nations is less than one-fiftieth of that found in the United States.[6, 7]

Given the limited human resources, most of the efforts to respond to the burden of mental health disorders in LMICs have focused on task-shifting strategies to expand treatment capacity. Such initiatives give community members or general medical providers the skills and support to deliver evidence-based depression treatment interventions.[8-10] Some efforts have trained lay health workers or non-specialist clinicians to deliver counseling interventions in, for example, Uganda, Tanzania, South Africa, Pakistan, and India.[11-18] Others have trained non-specialist clinicians, e.g. HIV clinicians or general care providers, to prescribe and manage antidepressant treatment in the context of regular medical care.[15, 19-21] [18] Both counseling and medication-based task-shifting approaches have demonstrated feasibility, acceptability, and efficacy in improving mental health outcomes in LMICs generally and sub-Saharan Africa specifically.

Despite the growing evidence base of task-shifting mental health interventions, rates of treatment for mental health disorders in LMICs are low. The proportion of individuals with a mental health disorder in LMICs who are not receiving treatment is estimated to be as high as 90%; the treatment gap for depression is even higher in many settings.[5] Several key factors are currently limiting the translation of this growing evidence base into actual health

system change. First, implementation science research is needed to close the knowledge gaps that policy makers face in trying to translate research to policy, for example what sorts of staffing and supervision structures are needed to sustain an evidence-based mental health intervention at scale? Relatedly, capacity to conduct implementation science research must be expanded among LMIC researchers. Finally, capacity among policy makers to interpret and apply implementation science research findings must be increased so that research can be efficiently used to inform health system redesign.

1.2 Study Rationale

Mental health disorders are among the leading causes of disease burden and disability worldwide. Globally, mental health disorders account for nearly a third of years lived with disability and are the fifth-leading cause of disability-adjusted life years.[1, 2] The global economic burden due to mental health conditions and related death and disability is expected to result in productivity losses of USD 16.1 trillion from 2010-2030.[22]

Both Malawi and Tanzania are currently in the process of revising their Mental Health Action Plans, and the potential for large impact from this project is high. In Malawi, the Non-Communicable Diseases and Mental Health Unit of the Ministry of Health was recently successful in expanding access to fluoxetine, a key antidepressant, across the country, based on the leadership of SHARP co-investigator [name]. The unit has also recently expanded non-communicable diseases clinics to treat hypertension and diabetes across the country under the leadership of SHARP Malawi PI [name], and a current high priority is the integration and expansion of mental health services within those clinics. The leadership in both Ministries of Health is eager to see the proposed scale-up study and capacity-building activities take place. Given the Mental Health Action Plans in place in both countries and the demonstrated commitment by the Ministries of Health to using research to guide efficient and meaningful expansion of services, the proposed activities will have a large and sustainable impact on mental health care.

The aims and objective of SHARP are significant because they directly address the knowledge and capacity gaps that are currently hampering broader scale-up of mental health services in Malawi and Tanzania. SHARP will build critical bridges between governmental, academic, and non-governmental actors involved in mental health service delivery and planning, provide key evidence to guide expansion of mental health services, and expand capacity to conduct, interpret, and utilize mental health-related implementation science research to address the mental health treatment gap in Malawi, Tanzania, and the broader region.

2.0 HYPOTHESES AND STUDY OBJECTIVES

2.1 Hypotheses

Our primary objective is to compare two different implementation strategies to facilitate ongoing MOH efforts to scale up evidence-based depression treatment within NCD care. Specifically, we hypothesize that:

H1. Compared to providers at clinics receiving the basic implementation package, providers at clinics receiving the enhanced implementation package will deliver depression treatment with greater fidelity.

H2. Compared to patients receiving care at clinics with the basic implementation package, patients receiving care at clinics with the enhanced implementation package will be more likely to achieve depression remission at 6 and 12 months.

H3. Compared to patients receiving care at clinics with the basic implementation package, patients receiving care at clinics with the enhanced implementation package will be more likely to have well controlled hypertension and diabetes at 6 and 12 months.

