3.2 Population

Patients at the participating NCD clinics who meet the following eligibility criteria will be invited to participate.

Inclusion criteria

1. Ages 18-65 years (antidepressant treatment considerations differ for those <18 or >65 years, and these age groups are expected to be very rare in the target clinics),
2. Current or new patient receiving care for either hypertension or diabetes from the NCD clinic at a study site listed in Section 3.1, and
3. Elevated depressive symptoms (PHQ-9 score ≥ 5).

Exclusion criteria

Patients will be excluded if they have a history of bipolar or psychotic disorder, or show emergent threat of self-harm.

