3.4 Sample Size

A total of 116 patients will be enrolled from each clinic to measure clinical outcomes over time, for a total sample of 1,160 patients recruited over a two-year period.

Sample size and power: Assumptions. Statistical power analyses are based on these assumptions: (1) two-sided statistical significance tests; (2) Type I error $\alpha=0.05$; (3) power ($1-\beta$) of 80%; (4) intraclass correlation coefficient (ICC) of 0.02 for the mental health outcome. For behavioral interventions, clinic-level ICCs normally range from <<0.01 to 0.04. For effect size, up to 30% of depressive episodes may remit without treatment. We assume that the basic implementation package may improve depression treatment, so we assume the incidence of depression remission to be 40% with the basic package. A difference of 15 percentage points or more in depression remission in the enhanced arm relative to the basic arm would be clinically meaningful and worth detecting. Therefore the study is powered to detect this difference. Based on extremely high retention success in prior studies and the short time frame of the primary outcome (3 months), 90% retention is assumed. Given these assumptions, we will enroll 116 participants per clinic from 10 clinics, or 1,160 participants overall. Fewer clinics would require a prohibitive sample size.

We will also complete qualitative interviews with 8 patients, 6 clinic directors, 6 Clinical Coordinators, 12 providers, 6 Friendship Bench counselors, 6 SHARP research assistants, and 3 MOH officials. These interviews will take place in Year 3 of the study. Given standard sample size guidelines for qualitative data collection, this sample size is expected to be sufficient for theme saturation in each group.

We will additionally conduct 16 cognitive interviews and 200 structured surveys with nurses, clinicians and peer friendship bench counsellors to evaluate providers' perceptions of stigma and acceptance towards individuals with mental health disorders. These

interviews and surveys will take place in Year 3 of the study. The desired sample size for cognitive interviewing, while adequate for the inclusion of variety of staff, reflects the expectation that data saturation will be reached with a relatively small number of participants. The desired sample size for structure interview is reflective of the expectation that approximately 10 participants are needed for every survey item in the measure.

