3.5 Data Sources

Data will come from the following sources:

1. Patient participants: The 1,160 patients will complete structured interviews, either in-person or via phone, with trained interviewers at baseline, 3, 6 and 12 months. Research interviewers will also measure blood pressure, blood glucose, height, and weight.
2. Qualitative interviews with patients: Additional information on acceptability of the depression treatment program will be gathered via in-depth interviews with a subset of patients (n=8).
3. Clinical records: Information on depression treatment delivery and fidelity will be abstracted from clinical records.
4. Clinic director, Clinical Coordinator, provider, Friendship Bench counselor, SHARP research assistant, and MOH interviews: Information about implementation strategy and intervention acceptability and fidelity from in-depth interviews with clinic directors (n=6), Clinical Coordinators (n=6), providers (n=12), Friendship Bench counselors (n=6), SHARP research assistants (n=6), and MOH officials (n=3). Cognitive interviews will be conducted with providers (n=8) and Friendship Bench counselors (n=4). Structured surveys will be conducted with providers, friendship bench counselors, and clinic leadership (n=200).
5. End point qualitative interviews at each of SHARP's study sites will focus on additional factors affecting implementation strategy fidelity like organization climate, organizational change, and barriers and facilitators to strategy implementation. Specifically, this information will be gathered from clinic directors (n=10), Clinical Coordinators (n=10), providers (n=10), and SHARP research assistants (n=10).

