4.0 STATISTICAL ANALYSIS PLAN

Analysis of implementation and effectiveness outcomes will be intent-to-treat comparisons between arms. Comparisons will be made using generalized estimating equation models with a log link and binomial error distribution to compare proportions. The design effect introduced by clinic-level randomization will be addressed using the bias-corrected robust variance estimate for GEE models recommended given the small number of clusters. A secondary, as-treated analysis will restrict the analysis to those who received a minimum

dose of the depression treatment program (e.g., at least three depression care management appointments).

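### H3 compares follow-up control of two diseases in a cohort entered on either one, at any level of control, and the planned model names no baseline covariate

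*Combined protocol and SAP*

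**What the plan says.** - **Endpoint.** Section 2.1 (H3) expects that enhanced-package patients "will be more likely to have well controlled hypertension and diabetes at 6 and 12 months". The matching objective in Section 2.2 names the same two conditions together. Neither place says whether this is one joint endpoint or two, or over which patients each is counted.
- **Entry.** Section 3.2 requires a "Current or new patient receiving care for either hypertension or diabetes from the NCD clinic". One disease is enough, established patients qualify, and nothing is required about how well the disease is controlled. Depression, by contrast, has an entry threshold: "Elevated depressive symptoms (PHQ-9 score ≥ 5".
- **Measurement.** Section 3.5 schedules patient interviews at baseline, 3, 6 and 12 months and adds: "Research interviewers will also measure blood pressure, blood glucose, height, and weight".
- **Analysis.** Section 4.0 states: "Analysis of implementation and effectiveness outcomes will be intent-to-treat comparisons between arms". The method is "generalized estimating equation models with a log link and binomial error distribution to compare proportions", with a small-sample-corrected robust variance for clustering. No baseline covariate and no disease-specific population is named.
- **Size.** Section 3.4 rests on depression remission alone. It gives no assumption for H3.

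**The concern.** H2 starts from patients who all have raised symptom scores. H3 does not start from patients who all have the disease in question, or who are all uncontrolled. Its follow-up proportion therefore depends on the arm and also on how many participants have each disease and how many were controlled when they enrolled. Both can differ between clinics, and ten clinics do little to average such differences out.

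Two things are at stake. The first is precision: baseline readings are strong candidates to explain follow-up control, and leaving them out keeps avoidable variation in the arm contrast. The second is sensitivity and interpretation: if the enhanced package mainly helps patients who are uncontrolled at entry, averaging over everyone shrinks the difference, and a pooled result does not say which disease moved.

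**Working it through.** **1. The plan's own figure (H2 only).** Inputs from Section 3.4: 40% vs 55%, "two-sided statistical significance tests" at 0.05, power 80%, ICC 0.02, 90% retention, 10 clinics; Section 3.0 gives 1:1 allocation, so 5 per arm.

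- Per arm before clustering: n = (1.960 + 0.842)² × (0.40×0.60 + 0.55×0.45) / 0.15² = 170.06.
- Per clinic: m = n(1 − ICC) / (5 − n×ICC) = 170.06×0.98 / (5 − 3.40) = 104.24.
- With retention: 104.24 / 0.9 = 115.8, so 116. The stated figure reproduces.
- Check: 116×0.9 = 104.4 analysed per clinic. Effective n per arm = 5×104.4 / (1 + 103.4×0.02) = 170.1. A pooled-variance normal approximation gives power 79%.

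No such figure exists for H3. Everything below rests on assumptions.

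**2. Noise from baseline imbalance.** Suppose the package has no effect, a share c is controlled at entry, follow-up control is s among those patients and u among the rest. The arm proportion is c×s + (1 − c)×u. Each percentage point by which c differs between arms moves the contrast by (s − u) points. With u = 40%, that is 1.00 − 0.40 = 0.60 points if s = 100%, and 0.85 − 0.40 = 0.45 points if s = 85%. Adjusting for baseline control removes this component to the extent that the model captures it.

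**3. Possible dilution.** Assume 40% vs 55% control among patients uncontrolled at entry, ICC 0.02 and 104.4 analysed per clinic. If patients controlled at entry all stay controlled in both arms, the difference is 15×(1 − c). If the package also helps them keep control (assumed 75% vs 85%), it is 15×(1 − c) + 10×c.

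| Controlled at entry (c) | No effect on keeping control: difference, power | 75% vs 85% keep control: difference, power |
|---|---|---|
| 20% | 12 points, 61% | 14 points, 74% |
| 40% | 9 points, 43% | 13 points, 69% |
| 60% | 6 points, 27% | 12 points, 65% |

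These powers use the normal approximation that reproduces the plan. With a t reference on 8 degrees of freedom the base power is 69% rather than 79%, and the middle column becomes 51.1%, 35.3% and 22.5%.

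**4. Price of separate denominators.** At 40% control in the basic arm and ICC 0.02, the difference detectable with 80% power (normal approximation) is 15.1 points in the full cohort. It is 16.1, 17.4 or 19.9 points if 70%, 50% or 30% of participants have the disease. The loss is moderate because, with five clinics per arm, between-clinic variation takes up much of the variance.

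**The case against.** A reader might infer that H3 counts patients whose status cannot change. The documents do not support that. H3 concerns *having* control at follow-up, so a patient controlled at entry can lose it, and keeping it counts as benefit. The last column of the table shows that most of the dilution then disappears.

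A reader might also infer that one-disease patients swamp the endpoint, for instance by spreading a diabetes effect over the whole cohort. H3 is not a diabetes-only endpoint. If a patient without diabetes scores as controlled for it, the joint endpoint still moves with that patient's hypertension. Entry requires care for at least one of the two diseases, so every participant has one on which the endpoint can move. Nor do the documents say that H3 is a single joint endpoint; a disease-by-disease reading is natural, and comparison by assigned arm is compatible with it. The unstated denominator is largely missing detail.

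Finally, Section 4.0 uses a robust variance suited to few clusters, so between-clinic variation enters the standard error. Chance imbalance and dilution cost precision and power; they do not bias the randomised comparison.

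All of this stands. What it leaves is that the model names no baseline covariate for outcomes whose baseline values the interviewers are set to measure, in a trial with few clusters.

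**Conclusion.** The point holds as a matter of efficiency and clarity. H3 is compared without a named baseline covariate, in a cohort of mixed disease and unrestricted baseline control. Avoidable noise follows from this in a comparison of 5 against 5 clinics. Dilution is possible but not demonstrated: it requires an effect concentrated in patients uncontrolled at entry and little or no effect on keeping control. Its size is unknown because the documents give no disease mix, baseline control rate, H3 effect or H3 ICC. The 12, 9 and 6 points are conditional illustrations; they do not estimate this trial's loss. The change is worthwhile mainly because it costs so little.

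**What to change.** **Section 4.0.** Adjust each H3 model for the participant's own baseline blood pressure or glucose, or for baseline control status. Section 3.5 has interviewers take these measurements and includes a baseline interview. It also allows interviews by phone, so state how a missing baseline reading is handled.

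**Sections 2.1 and 2.2.** State H3 as two comparisons: blood pressure control among participants under care for hypertension at enrolment, and glucose control among those under care for diabetes at enrolment. A participant with both counts in both. Membership is fixed at enrolment, so the comparison remains by assigned arm.

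**Cost.** This is analysis wording only, with no new data collection. Each comparison has a smaller denominator (step 4 of the working). Adding a covariate to a log-binomial model can cause convergence trouble, so name a fallback in advance, such as a log link with Poisson working variance and the same corrected robust variance. Neither change removes dilution from patients already controlled: they stay in the denominator, properly so, since keeping control is part of H3. If H3 results by arm have already been seen, the adjusted analyses should be labelled as specified afterwards.

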2.2 Study Objectives

Phase I (formative studies, not covered in this protocol)

Results from Phase I will inform the implementation of the Phase II research study comparing two different implementation strategies.

- We conducted in-depth interviews with providers, clinic directors, and Ministry of Health representatives to adapt the intervention to the NCD care context in Malawi.
- We conducted site visits to assess key contextual and structural characteristics of each clinic including organizational readiness for change, management support, patient panel size and demographics, number and training level of staff, staff-to-patient ratio, typical daily patient volume, hours of operation, and storage facilities for medications.

Phase II (Randomized Trial)

- Compare providers' fidelity of depression treatment between clinics receiving the basic implementation package vs. clinics receiving the enhanced implementation package.
- Compare patients' depression remission at 6 and 12 months between those receiving care at clinics with the basic implementation package vs. those receiving care at clinics with the enhanced implementation package.
- Compare patients' well controlled hypertension and diabetes at 6 and 12 months between those receiving care at clinics with the basic implementation package vs. those receiving care at clinics with the enhanced implementation package.

